5.11 Study Medication Use, Patient Instructions and Diary

At the baseline visit, [REDACTED] tubes of study medication from the subject kit box will be dispensed to enrolled subjects along with a diary card. Each subject will also receive a copy of written instructions, which detail the proper application method, storage requirement for the study medication and general instructions regarding the study [REDACTED]. The study staff will ensure that the subjects know how to properly apply the study medication and record each dose in the subject diary. The initial applications of the study medication will be done by the subject [REDACTED] under study site staff supervision during Visit 1/Day 1 (Baseline). Additionally, the study staff must ensure subjects understand the instructions for applying the study medication and refrigerate the study medication at home all times. The study staff should instruct the subject to apply both subsequent doses of the study medication at home once daily on Days 2 and 3 of study period preferably at approximately the same time.

[REDACTED] Subjects will be instructed by the study staff to contact the site for a replacement tube of medication **in the event a tube of medication is lost, contaminated or not refrigerated**. Additionally, a study staff will review the subjects' diary to confirm that only one single dose of study medication was applied before the fourth tube of study medication is dispensed to subjects and will record the reason for dispensing the tube in the source document and eCRFs.

A subject should only use [REDACTED] study medication daily for each application and should refrain from using the same tube even if it still contains study medication. At Visit 2/Day 4 the study medication will be collected to visually assess compliance. Compliance will also be determined from the diary card, in which the subject will be instructed to record all applications made or missed. After the compliance evaluation, empty, filled and partially used tubes will be collected and kept by the site.

At Visit 1, [REDACTED] cleanse the designated treatment area for the duration of the study following their normal daily routine. Subjects will wash the designated treatment area with the cleanser by using only the hands and pat dry with a soft towel [REDACTED] before applying the study medication. The study medication will be applied to the selected treatment area, up to one contiguous skin area of approximately 25 cm² area (e.g., 5 cm x 5 cm), using [REDACTED] unit dose tube. After spreading the study medication evenly over the treatment area, [REDACTED] Subjects should wash their hands immediately after applying the study medication gel and take care not to transfer the applied study medication gel during and after application to other areas, including the eyes. [REDACTED]

[REDACTED]

Subjects should continue to use the mild, non-abrasive, non-medicated cleanser to wash the treatment area located on the face or scalp provided by the study doctor or staff for the duration of the study. Subjects will be instructed to not use any other topical treatments or products other than the study medication gel in the selected treatment area.

Diary cards will be dispensed for each enrolled subject. The subjects will be instructed to complete the diary card after applying each daily dose of study medication. At Visit 2/Day 4, the study personnel will review the diary card to determine the subject dosing compliance, confirm use of any prohibited medications, assess AEs and a new diary will be dispensed to all subjects. At each subsequent visit, study personnel will review the diary card, to determine the subject use of any prohibited medications, assess AEs and dispense a new diary (a diary will not be dispensed at Visit 4/ Day 57). In addition, each study subject will be reminded to return all previously dispensed tubes (regardless of content) at Visit 2/Day 4 and the completed diary card at the next visit. Study personnel will schedule the subject's next visit prior to the subject's departure.

5.12 Visit Specific Procedures

The following sections outline the procedures required at each visit.

5.12.1 Visit 1/Day 1 (Baseline)

Prospective subjects will visit the study center and will be examined by the study physician or delegated staff. The following procedures will be performed at the baseline visit:

[REDACTED]

[REDACTED]

5.12.2 Visit 2/Day 4 (+1 day)

[REDACTED]

5.12.3 Follow-up Phone Call /Day 15 (± 3 days)

[REDACTED]

5.12.4 Visit 3/Day 29 (± 3 days)

[REDACTED]

5.12.5 Visit 4/Day 57 (± 2days) End of Study /Early Termination Visit

[REDACTED]

5.12.6 Unscheduled

An unscheduled visit is allowed at any time if in the investigator's opinion it is warranted. If the investigator assesses the subject's condition and determines that the subject's condition has worsened to the degree that it is unsafe for the subject to continue in the study, the subject may be discontinued from the study as a treatment failure, and a standard of care treatment

may be advised at the investigator's discretion. The following procedures may be performed at the Unscheduled/Early Termination Visit.

- [REDACTED]
- [REDACTED]
- [REDACTED]
- [REDACTED]
- [REDACTED]
- [REDACTED]
- [REDACTED]
- [REDACTED]

5.13 Summary of Assessments

The schedule of visits and procedures to be conducted at each visit are summarized in the Schedule of Study Procedures.

[REDACTED]	[REDACTED]	[REDACTED]	[REDACTED]	[REDACTED]	[REDACTED]	[REDACTED]
[REDACTED]	[REDACTED]	[REDACTED]	[REDACTED]	[REDACTED]	[REDACTED]	[REDACTED]
[REDACTED]	[REDACTED]	[REDACTED]	[REDACTED]	[REDACTED]	[REDACTED]	[REDACTED]
[REDACTED]	[REDACTED]	[REDACTED]	[REDACTED]	[REDACTED]	[REDACTED]	[REDACTED]
[REDACTED]	[REDACTED]	[REDACTED]	[REDACTED]	[REDACTED]	[REDACTED]	[REDACTED]
[REDACTED]	[REDACTED]	[REDACTED]	[REDACTED]	[REDACTED]	[REDACTED]	[REDACTED]
[REDACTED]	[REDACTED]	[REDACTED]	[REDACTED]	[REDACTED]	[REDACTED]	[REDACTED]
[REDACTED]	[REDACTED]	[REDACTED]	[REDACTED]	[REDACTED]	[REDACTED]	[REDACTED]
[REDACTED]	[REDACTED]	[REDACTED]	[REDACTED]	[REDACTED]	[REDACTED]	[REDACTED]
[REDACTED]	[REDACTED]	[REDACTED]	[REDACTED]	[REDACTED]	[REDACTED]	[REDACTED]
[REDACTED]	[REDACTED]	[REDACTED]	[REDACTED]	[REDACTED]	[REDACTED]	[REDACTED]
[REDACTED]	[REDACTED]	[REDACTED]	[REDACTED]	[REDACTED]	[REDACTED]	[REDACTED]
[REDACTED]	[REDACTED]	[REDACTED]	[REDACTED]	[REDACTED]	[REDACTED]	[REDACTED]
[REDACTED]	[REDACTED]	[REDACTED]	[REDACTED]	[REDACTED]	[REDACTED]	[REDACTED]

[REDACTED]	[REDACTED]	[REDACTED]	[REDACTED]	[REDACTED]	[REDACTED]	[REDACTED]
[REDACTED]	[REDACTED]	[REDACTED]	[REDACTED]	[REDACTED]	[REDACTED]	[REDACTED]
[REDACTED]	[REDACTED]	[REDACTED]	[REDACTED]	[REDACTED]	[REDACTED]	[REDACTED]
[REDACTED]	[REDACTED]	[REDACTED]	[REDACTED]	[REDACTED]	[REDACTED]	[REDACTED]
[REDACTED]	[REDACTED]	[REDACTED]	[REDACTED]	[REDACTED]	[REDACTED]	[REDACTED]
[REDACTED]	[REDACTED]	[REDACTED]	[REDACTED]	[REDACTED]	[REDACTED]	[REDACTED]
[REDACTED]	[REDACTED]	[REDACTED]	[REDACTED]	[REDACTED]	[REDACTED]	[REDACTED]
[REDACTED]	[REDACTED]	[REDACTED]	[REDACTED]	[REDACTED]	[REDACTED]	[REDACTED]

[REDACTED]

5.14 Screen Failures

A screen failure is a subject who received information about the study, including signing an informed consent, and possibly performing some study related procedures but was not enrolled, dispensed and applied study medication. Screen failures information will not be entered in the database and will not be included in any data analyses.

5.15 Protocol Deviations/Violations

This study will be conducted as described in this protocol except for an emergency situation in which the protection, safety, and well-being of the subject requires immediate intervention, based on the judgment of the investigator or a responsible, appropriately trained and credentialed professional(s) designated by the investigator. In the event of a significant deviation from the protocol due to an emergency, accident or mistake, the investigator or designee must contact Perrigo/Symbio contacts in Section 14 [REDACTED] at the earliest possible time.

[REDACTED]

[REDACTED]

[REDACTED]

[REDACTED]

5.16 Subject/Treatment Compliance

Subjects will apply the medication to the designated treatment area at approximately the same time once daily for 3 consecutive days. [REDACTED]

[REDACTED]

[REDACTED] Compliance will be determined from the diary card, in which the subject will be instructed to record all applications made or missed. The first and last dates of treatment should be recorded in the source document and eCRFs. The total number of applied and missed applications should also be recorded. Applications will be considered missed if the study medication was not applied on Day 1, Day 2 or Day 3 of the treatment period. [REDACTED]

[REDACTED] All used and unused tubes of study medication will be collected by the study site at appropriate visits or early termination.

5.17 Discontinuation/Withdrawal of Study Subjects

Subjects will be removed from the study for any of the following reasons:

- The subject withdraws his or her consent for any reason.
- The subject's condition has worsened to the degree that the investigator feels it is unsafe for the subject to continue in the study.
- Subject did not meet entry criteria.
- The subject's medication code is unblinded.
- An adverse event (AE) including intercurrent illness, occurs for which the subject desires to discontinue treatment or the investigator determines that it is in the subject's best interest to be discontinued.

[REDACTED]

Protocol No: PRG-NY-14-019

- The subject is lost to follow-up. The investigator will document efforts to attempt to reach the subject twice by telephone and will send a certified follow-up letter before considering that subject lost to follow-up. All attempts must be thoroughly recorded.
- The subject becomes pregnant during the course of the trial.
- Lack of efficacy (treatment failure)
- Investigator Discretion
- Significant protocol violation or non-compliance with the study protocol that could interfere with the effect or accurate assessment of the assigned study treatment.

After a subject has been discontinued, he/she will not be allowed to re-enroll in the study.

The reasons for a subject being discontinued will be documented in the source document, eCRFs and the enrollment log.

If a subject is discontinued from the study for any reason, the Visit 4/ Day 57 End of Study Visit/Early Termination Visit procedures should be completed and any outstanding data and study medication should be collected. Data, in addition to the primary reason for discontinuation and the date of removal, will be recorded in the source document and the End of Study eCRF.

[REDACTED]

[REDACTED]

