3 STUDY DESIGN

3.1 Type/Design of Study

Subjects in this multi-center, double-blind, randomized, vehicle-controlled, parallel-group study will be assigned [REDACTED] to test product, reference product, or vehicle, respectively. The study medication will be dispensed at Visit 1/Day 1 (Baseline) to subjects meeting all entry criteria. The assigned study medication will be applied topically [REDACTED] to the designated treatment area (up to one contiguous skin area of approximately 25cm² on the head region (face or scalp) once daily for three (3) consecutive days, avoiding contact with the eyes, mouth and other body areas during and after gel application.

Subjects will be healthy males and females, at least 18 years of age, with 4 to 8 clinically typical, visible and discrete, nonhyperkeratotic, nonhypertrophic Actinic Keratosis lesions within a contiguous 25cm² treatment area on the head region (face or scalp) excluding the nose. Visits to the study site are scheduled at Day 1 and Day 4, Day 29, and Day 57. There will also be a phone call at Day 15 to follow up on previously reported adverse events by the subjects.

At Visit 1/Day 1/Baseline written informed consent will be obtained. The subject's demographic profile, medical history, and prior/concomitant medication use will be recorded. A urine pregnancy test will be performed for all women of childbearing potential. A brief physical examination (including heart, lung and abdomen evaluations) including vital signs and height/weight will be recorded during baseline.

The subject's history of Actinic Keratosis will be evaluated at Visit 1/Day 1 (Baseline). A dermatological exam and Actinic Keratosis lesion assessment will be conducted at Visit 1/ Day 1(Baseline), and Visit 4/Day 57, and if necessary at an Unscheduled visit. Subjects who meet all of the inclusion and none of the exclusion criteria will be enrolled in the study, [REDACTED]

[REDACTED] and given a daily diary to complete. Instructions on proper treatment application and completion of the diaries will be provided to subjects and the rest of their visits will be scheduled. During the baseline visit, the study staff will demonstrate proper medication application to the subject and then observe the subject applying their initial application to ensure subjects understand the instructions. The study staff should instruct the subject to [REDACTED]

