6.2.5 Procedure for Breaking the Blind

The investigator, staff at the study site, study monitors, and data analysis/management personnel are blinded to the subject assignment. In the event of an emergency, the specific subject treatment may be identified by removing the overlay of the blinded label for each subject at each investigator site, which is attached to the study medication log. However, every effort should be made to maintain the blind. **The investigator must not scratch off the occluding layer of the label unless absolutely necessary to provide medical treatment to a subject in an emergency situation. When possible, the investigator site should inform Perrigo**

or designee. The reason for breaking the blind must be clearly documented in the source documentation and eCRFs and the subject discontinued from the study.

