Subjects will be admitted into the study only after written informed consent has been obtained and all of the inclusion and none of the exclusion criteria have been met. Randomization will be performed according to a computer generated randomization scheme where the treatment group designation has been assigned to the subject number. The treatment designation will remain blinded until the final database is closed. An independent third party generator will generate and hold the randomization code throughout the study. Randomized subjects will apply assigned treatment medication topically by spreading evenly [REDACTED] to the designated treatment area (up to one contiguous skin area of approximately 25cm² on the head region (face or scalp) once daily for three (3) consecutive days, avoiding contact with the eyes, mouth and other body areas during and after gel application.

Subjects will be scheduled for an office visit for Visit 1/Day 1 (Baseline), Visit 2/Day 4 (+1 days) (Post-Treatment Interim), Visit 3/Day 29 (±3 days) (Interim), and Visit 4/Day 57 (±2 days) (End of Study). Safety will be assessed by monitoring adverse events at each visit and during a Follow-Up Phone Call/Day 15 (±3 days).

4 Populations To Be Analyzed

Three subject populations are defined as follows:

- (1) An intent-to-treat (ITT) subject is any individual who: (a) was randomized into the study, and (b) received and applied at least one dose of study medication;
- (2) A modified intent-to-treat (mITT) subject is any individual who: (a) was randomized into the study, (b) met eligibility criteria, (c) received and applied at least one dose of study medication, and (d) had at least one post-baseline efficacy assessment;
- (3) A per-protocol (PP) subject, consistent with the protocol, is one that: (a) met eligibility criteria, (b) was randomized into the study, received and used study medication, (c) applied the study medication on Days 1-3 [REDACTED] (d) completed Visit 4/Day 57 (End of Study/Early Termination Visit) within the ±2 days visit window OR was discontinued from the study due to treatment failure [REDACTED] and (e) without significant protocol violations that could have interfered with the administration of the treatment or the precise evaluation of treatment efficacy.

[REDACTED]

[REDACTED]

5 Planned Analyses

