5.5 Efficacy Variables and Analyses

The primary efficacy measure is the proportion of subjects with clinical response of success defined as complete clearance (absence) of all clinically visible Actinic Keratosis lesions identified at the baseline visit and no new Actinic Keratosis lesions in the treatment area at Visit 4/Day 57.

Equivalent Efficacy

The compound hypothesis to be tested for clinical equivalence between test and reference is:

$$H_0: p_T - p_R < -0.20 \text{ or } p_T - p_R > 0.20 \text{ versus}$$

$$H_A: -0.20 \leq p_T - p_R \leq 0.20.$$

Where p_T and p_R are the proportions of subjects with clinical success at Visit 4/Day 57 for the test and reference products, respectively. The test product will be considered to be clinically equivalent to the reference product if the 90% confidence interval (CI) on the difference in their rates of clinical success, calculated by the Wald's method with Yates' continuity correction, is contained within the limits -0.20 to +0.20 for the PP population. Rejection of the null hypothesis supports the conclusion of therapeutic equivalence between the test and reference products for the primary efficacy variable.

[REDACTED]

Superiority

The hypotheses to be tested for superiority of the test and reference products over vehicle are:

$$H_0: p_T \leq p_V \text{ versus } H_A: p_T > p_V$$

$$H_0: p_R \leq p_V \text{ versus } H_A: p_R > p_V$$

Where p_T , p_R and p_V are the proportion of subjects with clinical success at Visit 4/Day 57 for the test, reference and vehicle products, respectively. The tests will be conducted independently for the test product and the reference product using two-sided, $\alpha = 0.05$, continuity-corrected Z-tests for the mITT subjects. Superiority will be established if the proportion of subjects with clinical success in the active treatment group is greater and statistically different than that in the vehicle. Rejection of the null hypothesis supports the conclusion of superiority of the test and reference products over the vehicle product for the primary efficacy variable.

[REDACTED]

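### Protocol 5.17 takes subjects out of the study for significant non-compliance or protocol violation, so the Day 57 lesion count used by the mITT superiority tests can go unobserved with no gain to PP

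*Protocol*

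**What the plan says.** Protocol 5.17 opens its list with "Subjects will be removed from the study for any of the following reasons". One entry is "Significant protocol violation or non-compliance with the study protocol that could interfere with the effect or accurate assessment of the assigned study treatment". The consequence is removal from the study, not only from treatment or from one analysis set. The same section says that after discontinuation for any reason "the Visit 4/ Day 57 End of Study Visit/Early Termination Visit procedures should be completed".

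Protocol 3.1 fixes when lesions are counted: "lesion assessment will be conducted at Visit 1/ Day 1(Baseline), and Visit 4/Day 57, and if necessary at an Unscheduled visit". No lesion count is scheduled at Visit 2/Day 4 or Visit 3/Day 29.

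SAP Section 4 deals with the same subjects at the analysis stage. PP requires dosing on Days 1 to 3 (criterion c) and, in criterion "e) without significant protocol violations that could have interfered with the administration of the treatment or the precise evaluation of treatment efficacy". Protocol 8.1.1 has matching criteria. mITT asks for randomization, eligibility, at least one applied dose and, as condition (d), at least one efficacy assessment after baseline. It sets no timing for that assessment.

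SAP 5.5 defines success at Visit 4/Day 57. Equivalence is decided in PP. On superiority it says "The tests will be conducted independently for the test product and the reference product using two-sided", and it specifies continuity-corrected Z-tests at the 0.05 level in the mITT subjects.

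**The concern.** Significant violation and non-compliance bear on how far a subject's data can be interpreted. The plan already has an instrument for that, the PP exclusion. Removing the subject from the study as well goes further: it ends follow-up in a trial where treatment lasts three days and the outcome is read eight weeks later. After Day 3 no study treatment is left to stop, and what is lost is the outcome.

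That outcome matters for mITT, where both active products are tested against vehicle. The loss may also be related to treatment. Protocol 5.10 foresees site reactions that lead to temporary stopping of study medication, and Protocol Section 7 says severe local reactions can occur. Skipped doses, and so removal, could be more common on active gel than on vehicle. The documents give no rates. Removed subjects also lose the remaining scheduled site-reaction scores and scheduled adverse-event questioning.

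**Working it through.** The plan gives no figure to reproduce: sample size, allocation, assumed rates and dropout are redacted. The check is a trace through the visible rules, then an illustration.

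**Timing**
- The last dose is on Day 3 (Protocol 3.1). Tubes and diary are first reviewed at Visit 2/Day 4 (Protocol 5.11).
- The Visit 4 window is 57 ± 2, that is Day 55 to Day 59.
- Removal at Day 4: 55 − 4 = 51 days before the window opens.
- Removal at Visit 3/Day 29: 55 − 29 = 26 days before.

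**What happens to a subject removed before Day 55**

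| | Lesion count at the exit visit | No lesion count |
|---|---|---|
| Post-baseline efficacy assessment | yes, at the exit date | none visible |
| mITT condition (d) | met | not met |
| mITT status | in, with an early count | out, after randomization |
| Day 57 outcome | not observed | not observed |
| PP, criteria (c) and/or (e) | already excluded | already excluded |

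In neither column is the Day 57 outcome observed, and in neither does removal change PP.

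**Size, left column, on assumed inputs**

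Assume 100 subjects on active and 50 on vehicle, with success of 30% and 5%. Assume a fraction x is removed in each arm and counted as failure. The difference becomes (0.30 − 0.05)(1 − x). With a = 0.30(1 − x) and v = 0.05(1 − x), power is Φ[(a − v − c − 1.96·SE₀)/SE₁]. SE₀ uses the pooled rate and SE₁ the separate rates. The constant c is 0 without continuity correction and ½(1/100 + 1/50) = 0.015 with it.

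| x | Difference (points) | Power, c = 0 | Power, c = 0.015 |
|---|---|---|---|
| 0 | 25.0 | 97.7% | 95.8% |
| 2% | 24.5 | 97.4% | 95.2% |
| 5% | 23.75 | 96.8% | 94.2% |
| 10% | 22.5 | 95.6% | 92.2% |

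Example, x = 0 and c = 0: SE₀ = √(0.2167 × 0.7833 × 0.03) = 0.0714 and SE₁ = √(0.21/100 + 0.0475/50) = 0.0552. Then (0.25 − 1.96 × 0.0714)/0.0552 = 1.99, which gives 97.7%.

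With success of 45% and 5%, removing 3% to 10% shrinks the 40-point difference by 40 × 0.03 = 1.2 to 40 × 0.10 = 4.0 points.

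**Size, right column, on assumed inputs**

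Suppose removed active subjects would have had only the vehicle success rate of 5%, and the remaining active subjects 30%. Leaving the removed ones out of mITT raises the active rate by x(0.30 − 0.05): 1.25 points at x = 5% and 2.5 points at x = 10%. The bias then favours the active product, opposite to the left column.

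**The case against.** The strongest reply is that the clause is narrower than it looks. It needs significant non-compliance that could interfere with effect or assessment, and no visible text says that a missed dose triggers removal. The visible text partly points the other way: Protocol 5.16 has missed applications recorded, PP criterion (c) handles them at analysis, and SAP 5.6 summarizes compliance for all ITT subjects. Text that might define the threshold is redacted in 5.15 to 5.17. Compliance is also reviewed later, so non-compliance found at Visit 4 can still come with a Day 57 count. All of this stands, and it limits how many subjects are affected. It does not remove the clause, which on its face ends study participation.

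Several stronger readings are tempting and are not supported:
- **That mITT keeps every removed subject.** Condition (d) drops those with no post-baseline count.
- **That removed subjects have no assessment.** Section 5.17 calls for end-of-study procedures at exit.
- **That the plan has no rule for them.** SAP 5.2 covers dropouts and missing data, but its text is redacted.
- **That adverse-event collection stops.** Protocol 7.3 and 7.3.1 continue follow-up of existing events and the reporting of some later serious ones.
- **That the code-break rule has the same flaw.** It is also on the list ("The subject's medication code is unblinded"), and Protocol 6.2.5 repeats it ("The reason for breaking the blind must be clearly documented in the source documentation and eCRFs and the subject discontinued from the study"). But 6.2.5 confines code breaking to emergency medical treatment, and any later lesion count would be made at a site that knows the assignment. The case for retaining those subjects is different and weaker.

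**Conclusion.** The point holds for significant protocol violation and non-compliance. Removal forfeits the Day 57 outcome for the mITT superiority tests and brings PP nothing that criteria (c) and (e) do not already provide. It is a cheap improvement to the design, not a threat to a trial conclusion. In the illustration, equal removal of up to 10% counted as failure costs at most 2.5 points of a 25-point difference. Power falls from 97.7% to 95.6% without continuity correction, or from 95.8% to 92.2% with it. Excluding subjects who have no count could instead favour the active arm by a similar amount.

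All rates, arm sizes and removal fractions here are assumed. The real number affected and the direction cannot be derived, because SAP 5.2 and parts of Protocol 5.15 to 5.17 are redacted. A reader might infer a risk to the equivalence decision. The documents do not support that, since it is made in PP, which leaves these subjects out anyway.

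**What to change.** In Protocol 5.17, delete significant protocol violation or non-compliance as a reason for removal from the study. State instead that these subjects are excluded from PP but keep the remaining scheduled contacts through the Visit 4/Day 57 lesion count, within ±2 days, unless they withdraw consent or another listed reason applies. Leave the code-break rule (5.17 and 6.2.5), the safety-based reasons and all treatment decisions as written. The PP and mITT definitions need no change.

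The cost is a short protocol amendment, and a few subjects who do not count in PP complete visits that are already scheduled.
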